6.1.5. End of Treatment and Follow-Up Period

The End of Treatment visit will be 7 days (± 2 days) after the last dose of TRC253.

The Follow-Up visit will be 28 days (± 7 days) after the End of Treatment visit. Study procedures to be performed at the follow-up visit are specified in the Schedules of Assessments ([Table 7](#) and [Table 8](#)). Patients who have unresolved study-related toxicities will have extended

follow-up once monthly until study treatment-related toxicities have resolved (baseline or \leq Grade 1) or are deemed irreversible.

Table 7: Part 1 Dose Escalation Schedule of Assessments

Study Procedures	Notes	Screening	Cycle 1 (7 days)		Cycle 2 (28 days)				Cycles 3+ (28 days)	End of Treatment	Follow-Up (EOT+28 days)
		Day -28	Day 1	Day 4	Day 1	Day 8	Day 15	Day 22	Day 1		
Screening/Administrative											
Sign main informed consent form	Informed consent must be obtained before any study-related procedures.	X									
Inclusion and exclusion criteria		X									
Brain MRI	To determine eligibility. If MRI is clinically contraindicated, a brain CT will be performed.	X									
Medical history and demographics		X									
Prior therapies		X									
Study Drug Administration											
Study Drug Administration	On extended PK days, no food should be consumed for at least 8 hr before and 4 hr after TRC253 dosing. On all other days, no food should be consumed for at least 2 hrs before and 1 hr after dosing. Patients will dose in the clinic on all PK days. Patients will track meal times on their home dosing logs.		X		Continuous daily administration from Cycle 2 Day 1 until one or more withdrawal criterion is met (see Section 7.4.3).						
Safety Assessments											
Physical examination	Full physical at screening, and targeted physical based on adverse events at subsequent visits. ECOG at screening.	X	X	X	X	X	X	X	X	X	X
Vital signs	BP, heart rate, respiration, and body temperature. In addition, on cycle 1 day 1, blood pressure and heart rate will be measured prior to dose administration and hourly (±15 minutes) for the	X	X	X	X	X	X	X	X	X	X

Study Procedures	Notes	Screening	Cycle 1 (7 days)		Cycle 2 (28 days)				Cycles 3+ (28 days)	End of Treatment	Follow-Up (EOT+28 days)
		Day -28	Day 1	Day 4	Day 1	Day 8	Day 15	Day 22	Day 1		
	first 6 hours following the first dose.										
Physical measurements	Height and weight at screening. Weight only is taken prior to each cycle and at EOT visit.	X			X				X	X	X

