Blood pharmacokinetic sampling	Plasma samples will be obtained pre-dose. On cycle 1 day 15, samples will be obtained pre-dose and 6 hours post-dose (+/- 15 min).			X	X	X (Pre-dose and 6 hours post-dose)	X	X	X	X
Biomarkers										
AR mutation testing	See lab manual for further instructions.	X						X (Cycle 5 only)	X	
CTC collection	Enumeration and molecular profiling. See lab manual for further instructions.			X				X (Every 3 cycles: C4, C7, etc.)	X	
Testosterone, free testosterone, DHT, estradiol, DHEA-S, androstenedione, and SHBG	The appropriate amount of serum should be drawn to be analyzed locally.		X (Testosterone only)	X				X (Every 3 cycles: C4, C7, etc.)	X	
Archival Tumor Tissue	If available		(X)							
Disease evaluations										
Serum PSA			X	X				X	X	
CT or MRI scan of the chest and abdomen/pelvis	EOT assessments do not need to be repeated if they were performed within 28 days while on treatment.		X					X (C3, then every 3 cycles: C6, C9, etc.)	X	
Radionuclide bone scan			X					X (C3, then every 3	X	

Study Procedures	Notes	Pre-Screening	Screening	Cycle 1 (28 days)				Cycles 2+ (28 days)	End of Treatment	Follow-Up (EOT+28 days)
			Day -28	Day 1	Day 8	Day 15	Day 22	Day 1		
								cycles: C6, C9, etc.)		
Ongoing review										
Concomitant therapy		Continuous from signing of informed consent through 28 days after EOT visit.								
Toxicity assessment/adverse events										

The allowable window for each visit within the cycle is ± 2 days unless otherwise stated.

The allowable window for Follow-Up visit and all scans is ± 7 days.

(X) for an assessment at the Follow-Up (EOT+28 days) visit indicates the assessment does not need to be performed if there were no abnormalities observed for the assessment at the End of Treatment visit.

Safety assessments (except for ECG) on C1D1 do not need to be repeated if they were completed within 7 days prior in screening.

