7.4.2. Discontinuation of Study Treatment

A patient's study treatment must be discontinued if the investigator believes that for safety reasons or tolerability reasons (e.g., adverse event or disease progression) it is in the best interest of the patient to discontinue study treatment. The follow-up visit will be 28 days (\pm 7 days) after the patient discontinues study drug. Patients who have unresolved study-related toxicities will have extended follow-up.

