11.2. PSA Response and Time to PSA Progression

Prostate-specific antigen will be assessed at Day 1 of each cycle and PSA response and Time to PSA Progression will be determined by PCWG3 criteria.

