14.3. Endpoint Definitions

PSA Response at Week 12

PSA response is defined as a $\geq 50\%$ decline from baseline according to PCWG3 criteria ([Appendix 2](#)). An additional PSA obtained at least 4 weeks later must show $\geq 50\%$ decline from baseline to confirm the response.

Time to PSA Progression

Time to PSA progression is measured from the start of treatment until the criteria for PSA progression according to the PCWG3 are met ([Appendix 2](#)). Patient without PSA progression will be censored at the last PSA assessment.

Radiographic Progression-Free Survival (rPFS)

Radiographic Progression-Free Survival (rPFS) is measured from the start of the treatment until the criteria for radiographic disease progression are met or death occurs, whichever is first. Patient will be censored at the last disease assessment when no rPFS event is observed.

Pharmacokinetic Parameters

Pharmacokinetic parameters of TRC253 will be derived from plasma concentration versus time data after single dose and repeat dose, as applicable. The pharmacokinetic parameters to be assessed are shown below. Other parameters may also be assessed.

C_{max}	Maximum observed plasma concentration for each patient
C_{min}	Observed plasma concentration at the end of dosing interval for each patient
t_{max}	Time of maximum observed plasma concentration
AUC_{τ}	Area under the plasma concentration-time curve from time zero to 24 hours (dosing interval) at steady state
AUC_{last}	Area under the plasma concentration-time curve from time zero to the last time measured
AUC_{∞}	Area under the plasma concentration-time curve from time zero extrapolated to infinite time calculated as $AUC_{last} + C_{last}/\lambda_z$, where C_{last} is the last observed measurable (non-BQL) concentration; extrapolations of more than 20.00% of the total AUC are reported as approximations
λ_z	Apparent terminal elimination rate constant, determined by linear regression using the terminal log-linear phase of the log transformed concentration vs. time curve
$t_{1/2term}$	Apparent terminal elimination rate constant, determined by linear regression using the terminal log-linear phase of the log transformed concentration vs. time curve

$t_{1/2\text{eff}}$	Effective half-life
R_A	Accumulation Index
CL/F	Total apparent oral clearance
V_{ss}/F	Apparent oral volume of distribution at steady state

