- Endpoints for delay/prevention/progression:
 - After decline from baseline: record time from start of therapy to first PSA increase that is $\geq 25\%$ and ≥ 2 ng/mL above the nadir, and which is confirmed by a second value ≥ 3 weeks later (i.e., a confirmed rising trend); the requirement for an increase of 5 ng/mL was decreased to 2 ng/mL, and the requirement for a 50% increase was reduced to 25%
 - Standards for reporting PSA progression date may not indicate a need to stop treatment
- Recording the duration of PSA decline is of little value
- No decline from baseline:
 - PSA progression $\geq 25\%$ increase and ≥ 2 ng/mL increase from baseline beyond 12 weeks
- Relate to mechanism of drug and anticipated timing of potential favorable/unfavorable effects on PSA, if present

APPENDIX 3. OUTCOME MEASURES FOR CLINICAL TRIALS IN PROSTATE CANCER: RESPONSE BY DISEASE MANIFESTATION ACCORDING TO PCWG3 [8]

General	
Endpoints for control/relief/elimination	Record changes in lymph nodes, lung, liver, adrenal, and CNS sites separately
	Record up to five lesions per site of disease.
	Record changes in size using waterfall plot.
	Use RECIST 1.1 with caveats: 
 • Confirm favorable change with second scan. Record changes in size using waterfall plot • Record complete elimination of disease at any site separately. Confirm favorable change with second scan • Record complete elimination of disease at any site separately
Nodes	
Only report changes in lymph nodes that were ≥ 1.5 cm in the short axis	
Record changes in pelvic (regional) nodes and extrapelvic (distant/metastatic) nodes separately	
Visceral	
Use RECIST 1.1 with caveats: 
 • Record changes in liver, lung, adrenal, and CNS separately • Only report changes in lesions ≥ 1.0 cm in the longest dimension 	
Nodal and Visceral	
Endpoints for delay/prevention/progression	Record changes in nodal and visceral (lung, liver, adrenal, and CNS) disease separately
	Use RECIST 1.1 but clearly record type of progression (growth of existing lesions and development of new lesions) separately by site The recommendations apply to both non-metastatic CRPC and metastatic CRPC
	Record up to five lesions per site of spread
	Report the proportion who have not progressed at fixed time points (6 or 12 months)
	Note that for some treatments, a lesion may increase in size before it decreases

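### A PSA rise after a decline that first appears at or just before End of Treatment has no scheduled PSA to confirm it, so time to PSA progression is censored

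*Combined protocol and SAP*

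**What the plan says.** **Progression rule.** Appendix 2 dates PSA progression after a decline at the first increase of at least 25% and at least 2 ng/mL above the nadir, "and which is confirmed by a second value" taken no sooner than 3 weeks afterwards. If PSA never fell, it asks for the same size of increase from baseline beyond 12 weeks and states no confirmation.

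**Censoring.** Section 14.3: "Patient without PSA progression will be censored at the last PSA assessment".

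**Sampling.** Section 11.2: "Prostate-specific antigen will be assessed at Day 1 of each cycle". Tables 7 and 8 also mark serum PSA at EOT. In both tables the Follow-Up cell of that row is empty. It is not marked with the bracketed X, which the footnote defines "for an assessment at the Follow-Up (EOT+28 days) visit" as an assessment that may be skipped if nothing abnormal was found at EOT.

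**Timing.** The footnote to both tables ("The allowable window for each visit within the cycle is") allows 2 days either side. Section 6.1.5: "The End of Treatment visit will be 7 days" (plus or minus 2) after the last dose, with Follow-Up 28 days (plus or minus 7) after EOT. Section 7.4.2 instead counts the same 28 days (plus or minus 7) "after the patient discontinues study drug".

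**Response rule.** For PSA response, section 14.3 adds: "An additional PSA obtained at least 4 weeks later must show" a decline of 50% or more. It gives no visit tolerance.

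**The concern.** An endpoint that needs confirmation needs a sample late enough to supply it. Here the last scheduled PSA can itself be the first sign of progression. The rules for such a patient are clear (no confirmation, so no event), but the censoring is informative: he leaves the risk set on or just after the day his PSA was seen to rise. To the extent that such rises are real, the Kaplan-Meier curve is too high and the median time to PSA progression, which section 14.8 reports for each expansion cohort, is too long.

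A later SAP can choose how to treat these patients. It cannot recover a PSA that was never scheduled.

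**Working it through.** **Inputs.** Confirmation at 21 days or more (Appendix 2). Day 1 visits every 28 days, each movable by 2 days (tables). EOT 5 to 9 days after the last dose (6.1.5). Follow-Up 21 to 35 days after EOT (6.1.5), or 21 to 35 days after stopping drug (7.4.2).

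**Step 1: rises followed by another Day 1 visit.** The gap between consecutive Day 1 visits is 28 - 4 = 24 to 28 + 4 = 32 days. If the window runs from the previous visit, it is 26 to 30 days. Both exceed 21, so these rises can be confirmed on treatment.

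**Step 2: rise first seen at EOT.** No later PSA is scheduled, so it can never be confirmed on schedule.

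**Step 3: rise on a Day 1 visit, last dose L days later, no further Day 1 visit.** EOT falls L + 5 to L + 9 days after the rise.
- L + 9 < 21 means L of 11 or less: EOT is never late enough.
- L + 5 of 21 or more means L of 16 or more: EOT is always late enough.
- L of 12 to 15: it depends on the day EOT is held.

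**Step 4: who is affected.** Section 7.4.3 withdraws for progression by PCWG3, which after a decline already requires a confirmed rise. The gap therefore concerns patients who stop for something else. Section 7.4.3 lists several such reasons, and section 2.4 reports three discontinuations for adverse events, two of them for QTcF prolongation. The documents do not say how many such patients had a rising PSA.

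**Step 5: scale per patient, not an estimate of the total.** Turning one censored patient into an event on the same date, with n at risk, multiplies the Kaplan-Meier curve from then on by (n - 1)/n, or less if other events fall on that date. Since n cannot exceed the cohort size, the relative drop is at least 1/15 = 6.7% in Cohorts 1 and 3 and at least 1/30 = 3.3% in Cohort 2, at the planned maximum sizes. The number of such patients is unknown, so no shift in the median is claimed.

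**Step 6: would a Follow-Up PSA close the gap?**
- Section 6.1.5: 21 to 35 days after EOT, so it always meets the 3-week rule. It is 26 to 44 days after the last dose.
- Section 7.4.2: from 21 - 9 = 12 to 35 - 5 = 30 days after EOT. Of the 15 x 5 = 75 combinations of allowed days, 35 fall short of 21.
- For a Day 1 rise with the last dose on or after that day, Follow-Up is at least 21 days later under either section.

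**Step 7: the response rule.** The plan's own figures (section 14.2) reproduce: P(at least 11 of 30 | 50%) = 0.9506, and the exact 95% interval for 15/30 is 31.3% to 68.7%. In Part 2, Week 12 is Cycle 4 Day 1 (day 85) and the next PSA is Cycle 5 Day 1. Of the 25 pairs of allowed visit days, 10 are under 28 days apart (2 of 5 offsets if the window runs from the previous visit). But the rule asks for a further PSA, not the next one:
- If the patient continues, Cycle 6 Day 1 is 56 - 4 = 52 to 56 + 4 = 60 days after Cycle 4 Day 1 and always qualifies.
- If he stops at Cycle 5 Day 1 after continuous dosing, his last dose is at least 23 days after Cycle 4 Day 1, so EOT is at least 23 + 5 = 28 days after it and qualifies.

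**The case against.** The strongest reply on progression is that nothing here is contradictory. Appendix 2 demands confirmation, section 14.3 censors without it, and ending PSA at EOT is a design choice. The affected group is narrow: a prior decline, a rise first seen at or near EOT, and stopping for another reason. The endpoint is secondary, section 14 plans no hypothesis test, and an off-drug PSA is an imperfect confirmer. All of this stands, and it is why the point is minor. It does not remove the fact that a real late rise cannot count, or that a cheap sample would let it.

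A reader might also infer something stronger: that the 4-week response confirmation conflicts with the 2-day visit window and that up to 40% of responses (10 of 25) could be lost. The documents do not support this. The 10 of 25 counts pairs of calendar days, not patients, and a continuously dosed patient with a short gap has a later qualifying PSA. What remains is a patient still at a 50% decline on days 24 to 27 but not at the first sample from day 28 on, whom the stated rule calls unconfirmed, and patients with drug holds, missed visits, loss to follow-up or withdrawn consent.

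Nor do the documents support reading the progression gap as affecting late rises generally: step 1 covers rises followed by another Day 1 visit, and progression without a prior decline has no stated confirmation.

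**Conclusion.** The concern holds for time to PSA progression, as a minor weakness. A post-decline rise first seen at EOT, or on a Day 1 visit with the last dose 11 or fewer days later, has no scheduled PSA that can confirm it, and section 14.3 censors the patient. The direction is towards a longer time to PSA progression. The size cannot be derived from the documents. This assumes visits in window and no unscheduled PSA; one is not forbidden, but none is required.

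The response confirmation rule is not in error. Section 14 defers details to a Statistical Analysis Plan, and how to classify an in-window next-cycle PSA taken 24 to 27 days later is a drafting note for that plan.

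**What to change.** 1. Add serum PSA to the Follow-Up column of Tables 7 and 8.
2. State in section 14.3 that this PSA is used only to confirm a rise first seen at or just before EOT, when taken at least 3 weeks after that rise and before any new anticancer therapy, and that it does not move the censoring date. Without the last clause, every patient without progression would gain off-drug follow-up time.
3. Reconcile the Follow-Up timing. Section 6.1.5 and both table headers count from EOT; section 7.4.2 counts from stopping drug. The choice decides whether the new PSA always meets the 3-week rule.
4. For all patients, including those already past Follow-Up, list unconfirmed last rises and report a sensitivity Kaplan-Meier estimate counting them as events on the date of the rise. With the main estimate, this brackets the effect of those rises without a new sample.
5. Keep the 4-week response rule. Loosening it in an open-label trial with 12 expansion patients already enrolled (section 2.4) is hard to justify. At most, add one SAP sentence on a next-cycle PSA taken 24 to 27 days later.

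**Cost.** A protocol amendment with a few sentences, one extra tube at a visit where PK blood is already drawn, one listing and one sensitivity estimate. The sample is off drug, so an anti-androgen withdrawal decline, which the inclusion criteria recognise for earlier anti-androgens, could hide a real rise. Values after new therapy cannot be used.

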14.4. Safety Analyses

All safety analyses are to be performed on data from the safety population, which is the same as all treated population. The baseline value for safety assessment is defined as the value collected at the time closest to, but prior to, the start of study drug administration. The safety parameters to be evaluated are the incidence, severity, and type of adverse events, clinically significant changes in the patient's physical examination findings, vital signs measurements, and clinical laboratory results. Exposure duration of investigational product and reasons for discontinuation of study drug will be tabulated.

14.4.1. Adverse Events

The verbatim terms used in the eCRF by the investigator to identify adverse events will be coded using the Medical Dictionary for Regulatory Activities. Treatment-emergent adverse events are adverse events with onset during the treatment period to 28 days after the last dose of study drug, or that are a consequence of a pre-existing condition that has worsened since baseline. All reported adverse events will be included in the analysis. For each adverse event, the percentage of patients who experience at least 1 occurrence of the given event will be summarized by treatment group. Adverse Event Reporting and graded according to the NCI-CTCAE (Version 4.03).

Summaries, listings, datasets, or patient narratives may be provided, as appropriate, for those patients who die, discontinue treatment due to an adverse event, or experience a severe or serious adverse event.

Specifically, the following adverse events will be summarized:

- Incidence of DLT (Dose escalation: Part 1)

-
- All adverse events
 - Grade 3 or greater adverse events
 - Serious adverse events (SAEs)
 - Adverse events leading to discontinuation of treatment
 - Adverse events leading to death

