6.1.3. Screening Period

Parts 1 and 2:

All patients must sign the main ICF prior to the conduct of any study-related procedures. Screening procedures will be performed up to 28 days before the first dose of drug.

During the Screening Period, medical history and eligibility criteria will be reviewed and a complete clinical evaluation will be performed, which includes a physical examination, vital signs measurements, physical measurements, and ECG. A brain MRI (or if contraindicated, CT) scan will be performed to determine eligibility.

Laboratory tests (performed at the local laboratory) noted in the inclusion criteria (Section 7.2) must be within the limits specified in the inclusion criteria prior to the start of dosing.

Prior therapies will be recorded.

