12.1.1. Adverse Events

Adverse events that occur between the signing of the informed consent through 28 days following the last dose of study drug will be recorded. All patients who receive at least 1 dose of study drug will be considered evaluable for safety assessment. Any clinically relevant changes occurring during the study must be recorded on the Adverse Event section of the eCRF.

Adverse events reported by the patient (or, when appropriate, by a caregiver, surrogate, or the patient's legally acceptable representative) during the study will be followed by the investigator as specified in [Section 12.3](#), Adverse Event Reporting.

Abnormal and clinically significant laboratory tests should be recorded as adverse events. To meet the definition of clinically significant, the test result generally requires a change in medical management (e.g., new medication, unplanned treatment, additional tests, etc.).

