12.3.2. Adverse Event Reporting Period

The AE reporting period for this trial begins with informed consent and ends following the completion of the 28 day follow-up visit or at least 28 days after the last dose of TRC253 study drug is administered, whichever occurs later. Data for patients who screen fail will not be collected in the clinical database. However, if a screen fail patient experiences an AE that is considered related to study conduct or study procedures during the screening period, the event will be tracked on the Patient Screening Log and the event will be assessed for reportability. All events that occur following enrollment, even if the patient does not go on to receive study treatment, will be entered on CRFs. AEs occurring prior to the initiation of the study treatment will be considered “baseline-emergent adverse events” and will be recorded on the corresponding CRFs.

All AEs that occur in trial patients during the AE reporting period specified in the protocol must be reported to TRACON, whether or not the event is considered study treatment-related. In addition, any known untoward event that occurs beyond the AE reporting period that the Investigator assesses as a suspected adverse reaction to the investigational medication/product should also be reported as an AE.

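### Section 14.4.1 defines treatment-emergent AEs but ties no table to them; read literally, pre-dose events in treated patients would enter the main AE incidence tables

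*Combined protocol and SAP*

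**What the plan says.** Section 14.4.1 of the protocol opens with a definition: "Treatment-emergent adverse events are adverse events with onset during the treatment period to 28 days after the last dose of study drug", or events reflecting a pre-existing condition that has worsened since baseline. The next sentence reads "All reported adverse events will be included in the analysis". The one after that gives the measure: "the percentage of patients who experience at least 1 occurrence of the given event will be summarized by treatment group". Six summaries follow: DLTs (Part 1), all AEs, Grade 3 or greater, serious, leading to discontinuation of treatment, and leading to death. None is limited to TEAEs. The safety analyses in the Synopsis list the same groups without a restriction.

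The collection window is wider than the TEAE window at both ends.

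- **Start.** Section 12.3.2 says "The AE reporting period for this trial begins with informed consent", and Section 12.1.1 agrees: "Adverse events that occur between the signing of the informed consent through 28 days following the last dose of study drug will be recorded". Section 6.1.3 adds: "Screening procedures will be performed up to 28 days before the first dose of drug".
- **End.** The schedules of assessments (Tables 7 and 8) collect AEs "Continuous from signing of informed consent through 28 days after EOT visit". Section 12.3.2 also asks for suspected reactions that occur after the reporting period.

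Section 12.3.2 gives pre-dose events a class of their own: "AEs occurring prior to the initiation of the study treatment will be considered" baseline-emergent, and they are recorded on the case report forms. Section 14 never mentions that class. Section 14.4 sets the safety population as all treated patients.

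**The concern.** A patient may have a symptom that starts and resolves during screening and then be dosed. That patient is in the safety population and the event is a reported AE. Under the literal sentence in 14.4.1 it counts toward the percentage of patients with that term in his dose group or cohort, although he had not yet taken TRC253.

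AE incidence is part of a primary endpoint (Section 4.1), and there is no comparator arm to carry the same background. The terms also overlap. Appendix 1 lists diarrhea and lower-extremity edema among events expected from the disease, while Section 2.5.1 lists diarrhea and peripheral edema among effects that TRC253 might cause. Pre-dose disease symptoms could therefore sit in the same table rows as possible drug effects. The laboratory and ECG summaries (14.4.2, 14.4.3) are expressed as change from baseline; the AE tables have no equivalent separation.

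**Working it through.** **Which tables are exposed**

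- *All, Grade 3 or greater, serious:* no time window is stated, so a pre-dose event in a treated patient qualifies.
- *DLT:* Section 5.2 counts 28 days from Cycle 2 Day 1, so a pre-dose event cannot enter.
- *Leading to discontinuation of treatment:* treatment must have started, so an event that began before dosing would rarely qualify.
- *Leading to death:* a treated patient whose fatal event began before the first dose would be rare.

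**Direction and possible size**

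The plan gives no figure for this point and no pre-dose AE rate. Let p be the on-treatment incidence of a term and q the probability of the same term before dosing in a treated patient. If the two are independent:

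- incidence from TEAEs only = p
- incidence from all reported AEs = p + (1 − p)q
- excess = (1 − p)q, which is never negative

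Anchor values for p come from the drug-related events reported in the ongoing study results (Section 2.4): 2/34 = 5.88%, 7/34 = 20.59% and 22/34 = 64.7%, rounded to 6%, 21% and 65%. The 95% row is an assumed any-AE rate. These values only set the scale. All values of q are assumptions.

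| p | q = 0 | q = 2% | q = 5% | q = 10% | q = 20% |
|---|---|---|---|---|---|
| 6% | 0 | 1.9 | 4.7 | 9.4 | 18.8 |
| 21% | 0 | 1.6 | 3.95 | 7.9 | 15.8 |
| 65% | 0 | 0.7 | 1.75 | 3.5 | 7.0 |
| 95% | 0 | 0.1 | 0.25 | 0.5 | 1.0 |

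(Excess in percentage points.) For example, at p = 6% and q = 5%: 0.94 × 0.05 = 4.7 points. With p = 6% and q = 2%, 5%, 10% or 20%, the expected number of extra patients is 1.1, 2.8, 5.6 or 11.3 among 60 in Part 2, and 0.3, 0.7, 1.4 or 2.8 in a cohort of 15.

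A constant-risk version behaves the same way. Assume 4 weeks of screening, 12 on drug and 4 of follow-up, with risk h per 4 weeks. TEAE incidence is 1 − (1 − h)^4 and all-reported incidence is 1 − (1 − h)^5. For h = 5%, 10% and 15%, incidence rises from 18.5% to 22.6%, 34.4% to 41.0% and 47.8% to 55.6%.

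**Why these figures lean high**

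- The constant-risk version uses a full 4 weeks of screening. Section 6.1.3 makes 28 days a maximum.
- It also assumes equal ascertainment before and after dosing. Section 12.3.1 requires patients to be questioned about AEs only at visits after treatment starts.
- Both versions assume independence. A patient with a symptom before dosing is likelier to have it on treatment and is then counted once anyway. If every such patient also had it on treatment, the excess would be zero.

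**The other end of the window**

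Section 6.1.5 places the End of Treatment visit 7 days (±2) after the last dose. Collection to 28 days after that visit ends about 7 + 28 = 35 days after the last dose, against 28 days in the TEAE definition.

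**The case against.** The best defence is that the sentence does not mean what a literal reader takes from it. It follows directly on the TEAE definition and may mean only that events count whatever their judged cause, as Sections 12.2 and 12.3.2 require for reporting. Pre-dose events have their own class in 12.3.2, so they can be identified. Section 12.3.6 groups AEs for analysis into suspected reactions and non-related events, and a pre-dose event could not credibly be a suspected reaction. Section 12.3.9 records a rise in grade as a new AE, so a pre-dose event that worsens on drug is properly treatment-emergent. Section 14 calls itself a general description and leaves details to a Statistical Analysis Plan.

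Much of this stands. A reader might infer that the plan attributes pre-dose events to TRC253 and so inflates the primary safety result by a material amount. The documents do not support that: no section makes the attribution, and no pre-dose rate is given from which to size an inflation.

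What remains is that nothing in Section 14 removes these events. The baseline-emergent label governs recording, none of the five AE tables other than DLT is limited to related events, and the inclusion sentence is affirmative and unqualified. No separate analysis plan text is in the document supplied, so whether it settles the matter cannot be seen. If it restricted the tables to TEAEs, it would depart from the wording of 14.4.1.

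**Conclusion.** The point holds as a defect in the stated analysis rule. Followed literally, 14.4.1 would put baseline-emergent events in treated patients into the tables of all, Grade 3 or greater and serious AEs. The direction is upward. The size is unknown: zero without pre-dose events, and from under 1 to about 19 points per term across the non-zero values tabulated, which rest on assumed pre-dose risks and independence. Rare terms move most; an any-AE rate near 95% moves by at most about 1 point.

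It is less than a mandatory correction. Section 14 plans no hypothesis test, no threshold depends on AE incidence, DLT decisions use their own window, and the RP2D has already been chosen. Onset dates would allow the restriction at any time before reporting.

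**What to change.** Replace the inclusion sentence in 14.4.1 with the following, and align the safety analyses in the Synopsis:

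> Incidence summaries include treatment-emergent AEs, regardless of causality, plus any later AE assessed as at least possibly related to TRC253; baseline-emergent AEs (onset before first dose and not worsened on treatment) are listed separately.

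The clause on later events is needed. A bare TEAE restriction would move suspected reactions arising after day 28 out of the incidence tables, although the schedules and Section 12.3.2 have them collected, and Section 5.2 anticipates a long half-life.

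The cost is one sentence and one extra listing, with no new data. Reported AE percentages may be slightly lower than under the all-reported rule.
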